4.3. Procedures

4.3.1. Data collection and quality of information

Once the approval of the ethics committee and INVIMA has been obtained, the screening and randomization process will be carried out by a team made up of the study investigators and those they designate. This team will be previously trained in every detail of the protocol. The inclusion of research participants and the collection of their data will be done consecutively as cases are identified in Valle del Cauca through the database of the laboratory of the Departmental Health Secretariat.

To collect the information, a pre-designed format will be used exclusively for this purpose, that includes the variables necessary to meet the objectives of the study.

This information will be entered into a database by trained personnel with extensive experience in this process.

Data input to the database will be detailed, performing range checks and ensuring consistency and veracity.

4.3.2. Study Procedures

The following procedures have been designed to meet the objectives of the study, reducing interaction between study personnel and research participants with COVID-19:

Once a subject with a positive antigen detection test or PCR for SARS-CoV-2 / COVID-19 has been identified, the principal or sub-investigator will contact the subject by telephone to provide study information through the telephone informed consent process. Subjects who express interest will be surveyed to obtain clinical and socio-demographic data and will be personally visited at their home or hospitalization site to sign the informed consent form in the presence of two witnesses.

At the screening visit, demographic data will be confirmed, informed consent will be signed, a blood sample will be obtained for liver enzyme evaluation, a pregnancy test (for women of childbearing age) and the participant's weight will be measured.

At the randomization visit, it will be determined whether or not the subject meets the selection criteria, including verification of liver enzyme result and pregnancy test (for women of childbearing age). Once it is defined that the subject meets the selection criteria. The research participant will be randomized, the necessary clinical data will be obtained, vital signs will be taken, and the investigation product will be initiated.

The administration of the research product will be done by self-administration in case of outpatient research participants, and in the case of hospitalized participants the administration instructions will be given to the subject and / or the health personnel who attends him/her, complying with the requirements of the institution.

Research participants will be contacted daily by phone call to remind them to take the research product, assess drug adherence, and detect adverse events to the research product.

4.3.3 Table of visits and follow-ups

| Visit number (V) | Screening | Randomization | Phone call 1 | Phone call 1 | Phone call 1 | Phone call 1 | Phone call 1 | Phone call 1 | Phone call 1 | Phone call 1 |
|---|------------|---------------|-----------------|-----------------|-----------------|-----------------|-----------------|-----------------|-----------------|-----------------|
| Study deadlines | SCR | D1 | D2 | D3 | D4 | D5 | D8 | D11 | D 15 | D 21 |
| Intervals (days) | | | | | | | ±1 | ±1 | ±1 | ±1 |
| Signed informed consent form | X | | | | | | | | | |
| Inclusion/exclusion criteria | X | X | | | | | | | | |
| Assignment of the research participant number | X | | | | | | | | | |
| Demographic Data | X | | | | | | | | | |
| Medical background check | | X | | | | | | | | |
| Weight | X | | | | | | | | | |
| Vital signs and pulse oximetry | | X | | | | | | | | |
| Calculation of NEWS -2 score: | | X | | | | | | | | |
| Collection of clinical data | | X | | | | | | | | |
| Urine sample to evaluate pregnancy | X | | | | | | | | | |

| | | | | | | | | | | |
|---|-----------------------|----------|----------|----------|----------|----------|----------|----------|----------|----------|
| Blood Sample to evaluate Hepatic enzymes ² | X ² | | | | | | | | | |
| Randomization | | X | | | | | | | | |
| Dispensing and initiating medication/placebo | | X | | | | | | | | |
| Evaluation of the 7-point ordinal scale | | X | X | X | X | X | X | X | X | X |
| Assessment of secondary outcomes - Pt. at home or hospitalized? - Has required oxygen? - Has required ICU? - Vital status - Persists with fever? | | X | X | | | X | X | X | X | X |
| Collection of Serious Adverse Events (SAE) | | | X | | | X | X | X | X | X |
| Pharmacotherapeutic Adherence | | X | | | | X | | | | |
| Remember the need to take the investigation product | | | X | X | X | X | | | | |
| Collect symptoms reported to the admin of the investigation product | | | X | X | X | X | X | X | X | X |
| Record of completion | | | | | | | | | | X |

¹ In the case of hospitalized research participants, the study staff will personally visit the subject and/or contact the physician in charge by telephone, and/or through the medical history will obtain the necessary information and thus be able to determine primary or secondary outcomes

² It will not be necessary to collect the liver enzyme sample if there is a recent result no more than 3 days prior to selection.

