4.1.5.2. Secondary outcomes to be evaluated

- To determine the time to deterioration in two or more points of the 7-point ordinal scale in the two study groups.
- To determine the clinical state, using the 7-point ordinal scale, on days 2, 5, 8, 11, 15, and 21.
- The proportion of subjects requiring hospitalization, use of supplemental oxygen > 24 hours, admission to the ICU, or dying within 21 days in the two trial groups.
- The duration of supplemental oxygen in each arm of the study.
- The duration of hospitalization in each arm of the study.
- The duration of stay in the ICU in each arm of the study.
- The duration of fever (axillary temperature > 38C or subjective feeling of fever) in each arm of the study.
- Proportion of subjects who develop adverse events associated with the study drug.
- Proportion of subjects who required discontinuation of medication due to adverse events.

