4.3.5 Follow up

To evaluate the evolution of the research participants and determine safety and efficacy according to the primary and secondary outcomes, subjects will be called on days 2, 3, 4, 5, 8, 11, 15 and 21 to fill out a questionnaire. In the event that the research participant requires hospitalization, the research participant will be visited personally to extract the information from the medical record. On the 21st day, the study will finish the evaluation of primary and secondary outcomes. In the case of hospitalized research participants, follow-up will continue until the end of hospitalization to determine their vital status.

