4.3.7 Measurement of Security Parameters

On the day of the screening visit, all participants will have their liver enzymes measured. The research participant will not be randomized and therefore will not be included in the study if these are elevated > 1.5 times normal values.

In follow-up calls (days 2, 3, 4, 5, 8, 11, 15, and 21), research participants will be asked about symptoms that have historically been reported in subjects receiving ivermectin (uncontrollable shaking of a body part, dizziness, loss of appetite, nausea, vomiting, stomach pain or bloating, diarrhea, constipation, weakness, drowsiness, chest discomfort, swelling (face, arms, hands, feet, ankles, or lower legs), and other symptoms, pain and swelling in joints, painful and swollen glands in the neck, armpit, or groin, fast heartbeat, eye pain, blurred vision, redness or tearing, swelling (face, arms, hands, feet, ankles or calves), pain and swelling in the joints, painful and swollen glands in the neck, armpit or groin, fast heartbeat, pain in the eyes, blurred vision, redness or tearing, swelling of the eyes or eyelids, abnormal

sensation in the eyes, fever, blisters or peeling of skin, rash, hives, and itching) to complete the information requested by the data collection form. The proportion of research participants with adverse events in both arms will be compared.

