4.2. Secondary outcomes

-Proportion of cases with deterioration in two or more points of the 8-point ordinal scale in the two study groups. Proportion of subject who reported an increase in disease severity of 2 or more points on the 8-point ordinal scale relative to the randomization visit.

-Proportion of cases that required hospitalization, use of supplemental oxygen > 24 hours, and admission to the ICU.

-Duration of hospitalization, use of supplemental oxygen and duration of stay in ICU in each arm of the study.

-Clinical state, using the 8-point ordinal scale, on days 2, 5, 8, 11, 15, and 21.

-Proportion of cases who develop fever (axillary temperature > 38°C or subjective feeling of fever) in each arm of the study and duration of fever. Number of days from the randomization visit to an axillary temperature <38°C.

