6.2. Secondary outcomes

Secondary outcomes, hospitalization requirement, ICU or oxygen supplementation and deterioration in more than two points on the scale of clinical results will be analyzed through a Kaplan Meier estimate. Hazard ratio will be estimated by Cox proportional-hazard model. In addition, a logistic regression model in which each secondary outcome will be considered as the dependent variable (1: Event, 0: No event) and the intervention groups as the independent variable (1: ivermectin, 0: Placebo) will be used.

For each outcome, the odds ratio (OR) and its respective 95% CI will be reported. An OR > 1 is indicating favorable results in favor of placebo and an OR <1 in favor of ivermectin. In case of low frequency of individual outcomes, a combined variable will be created using need for hospitalization (general floor or ICU) and need for oxygen (by nasal cannula or mechanical ventilation) and will be analyzed using a logistic regression model reporting the OR with its 95% CI.

Evaluation of the effect of the treatment in each study visit using the 8-point ordinal scale will be estimated using the proportional OR with its respective 95% CI with an ordinal logistic regression. In this step, the 8-point ordinal scale will be inverted in its score, where 0 will correspond to death and 7 to a subject without symptoms. Thus, a proportional OR > 1 will indicate an effect in favor of ivermectin. The 95% confidence interval of the median difference in duration of fever and length of hospitalization or oxygen use will be estimated by bootstrap estimators.

6.3. Sensitivity Analysis and Modification of the Effect for the Primary outcome.

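### The fever-duration item is not scheduled on D3 and D4, no temperature is scheduled after D1, and the plan does not say what dates the end of fever

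*Supplement*

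**What the plan says.** **Outcome.** Protocol 4.1.5.2 lists as a secondary outcome: "The duration of fever (axillary temperature > 38C or subjective feeling of fever) in each arm of the study". SAP 4.2 defines it as "Number of days from the randomization visit to an axillary temperature <38°C". SAP 6.2 puts a confidence interval on the contrast: the "median difference in duration of fever and length of hospitalization or oxygen use will be estimated by bootstrap estimators".

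**Schedule.** Protocol 4.3.5 says that "subjects will be called on days 2, 3, 4, 5, 8, 11, 15 and 21 to fill out a questionnaire". In table 4.3.3 the secondary-outcome row, which ends with the fever question, reads "Persists with fever? | | X | X | | | X | X | X | X | X". The columns run screening, D1, D2, D3, D4, D5, D8, D11, D15, D21, so the two blanks after D2 are D3 and D4. The ordinal scale is marked on both days. The row for vital signs and pulse oximetry is marked at D1 only.

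**Safety questions.** Protocol 4.3.7 says: "In follow-up calls (days 2, 3, 4, 5, 8, 11, 15, and 21), research participants will be asked about symptoms". The list includes fever ("sensation in the eyes, fever, blisters or peeling of skin, rash, hives, and itching"). The matching table row is marked from D2 onward, D3 and D4 included: "Collect symptoms reported to the admin of the investigation product | | | X | X | X | X".

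**The concern.** Fever duration was added as an indirect marker of the drug's antiviral capacity (justification for Amendment 2 in the summary of protocol changes). It is the secondary outcome for which the exact end day matters most, and the item written for it skips two calls inside the 5-day dosing period.

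Three gaps combine:

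- The efficacy item is silent on D3 and D4.
- The safety list does ask about fever on those days, but as a possible drug-related symptom. SAP 4.3 uses the same list for adverse events. Neither document says that these answers feed fever duration.
- The SAP's end of fever is a temperature below 38°C, yet no temperature is scheduled after randomisation. The protocol also counts a subjective feeling of fever, and the SAP rule gives no end point for a participant whose fever was only subjective.

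The analyst therefore has to choose a derivation rule that the plan does not supply. One natural choice, the next scheduled efficacy item, gives a coarse grid for a difference of medians.

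**Working it through.** The documents give no expected fever duration, febrile proportion or target difference, so there is no planned figure to reproduce. The check is what the schedule does to a known one-day difference.

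**Inputs from table 4.3.3.** Fever item after randomisation: D2, D5, D8, D11, D15, D21. With the change: D2, D3, D4, D5, D8, D11, D15, D21.

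**Assumed rule.** Let T be the first afebrile day. Recorded day = first scheduled fever item on or after T, with no end date recalled. The plan does not state this rule; it is what follows if the efficacy item is the only source.

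**Step 1: enumeration.** One arm is a day faster than the other.

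| First afebrile day, slower → faster | Recorded, current schedule | Difference | Difference with D3 and D4 added |
|---|---|---|---|
| 3 → 2 | 5 → 2 | 3 | 1 |
| 4 → 3 | 5 → 5 | 0 | 1 |
| 5 → 4 | 5 → 5 | 0 | 1 |
| 6 → 5 | 8 → 5 | 3 | 3 |
| 7 → 6 | 8 → 8 | 0 | 0 |
| 8 → 7 | 8 → 8 | 0 | 0 |

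T = 3, 4 and 5 share one recorded value. A one-day shift shows as 0 inside a gap and as 3 across a call day.

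**Step 2: whole distributions.** Assumed lognormal durations, log-SD 0.4 and 0.7, slower arm's median first afebrile day 3 to 7, faster arm one day earlier (not before day 2). The true median difference is 1 throughout.

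| Slower arm's median first afebrile day | Median difference, current | Median difference, D3 and D4 added |
|---|---|---|
| 3 | 3 | 1 |
| 4 | 0 | 1 |
| 5 | 0 | 1 |
| 6 | 3 | 3 |
| 7 | 0 | 0 |

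Both log-SDs gave the same medians. The difference in recorded means on the current schedule was 0.96 to 1.48 days, against true values of 0.66 to 1.00. It is the median that jumps; the mean is not driven to zero.

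**Step 3: trial-sized samples.** Assumed 100 febrile participants per arm, gamma durations with shape 3, 2,000 simulated trials per case. Durations are days from D1, so the current grid is 0, 1, 4, 7, 10, 14, 20.

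| True medians (days) | Current schedule | D3 and D4 added |
|---|---|---|
| 2 vs 3 | difference 0 in over 99.9% of runs | 0 in 21%, average 1.0 |
| 2.5 vs 3.5 | 0 in 95–96% | 0 in 2% |
| 0.7 vs 1.7 | average 3.0, never 0 | average about 1.0 |
| 1 vs 2 | 0 in about 45%, at least 3 in about 45% | average about 1.0, 0 in about 22% |
| 3.5 vs 4.5 | average 2.7 | average 2.8 |
| 5 vs 6 | 0 in about 97% | 0 in about 97% |

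The extra marks repair endings up to D5. Later endings stay on the 3-day and wider grid and need a recorded date.

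**The case against.** The strongest reply is that fever is in fact asked about on D3 and D4. Section 4.3.7 puts it on the list for every call, the symptom row is marked on both days, and 4.3.5 says that the calls on all eight days serve the primary and secondary outcomes. Because subjective fever counts under the protocol definition, a yes or no answer on those days would be usable. This stands. A reader who looks only at the efficacy row might infer that no fever information exists for D3 and D4, and the documents do not support that. What remains is that no rule says these answers date the end of fever, and they carry no temperature.

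Second, nothing fixes duration at the next call day. The SAP defines it by an event, the data collection form is not among the documents, and an end date could be asked at D5. Records can date fever for inpatients, and the calls from D8 on have a ±1 day window. This also stands: the grid values are a consequence of one possible rule. But the plan does not require an end date either.

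Third, a reader might infer that a one-day benefit must show as zero. It need not: Steps 1 to 3 give 0 or about 3 depending on where the medians fall, so the error can also exaggerate. Nor do the documents show that fever usually ends within the dosing period. They give no fever durations, and enrolment is allowed up to 7 days after onset.

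**Conclusion.** The point holds as a gap in measurement and definition for one secondary outcome. The efficacy fever item is unscheduled on D3 and D4 although the calls are made, no temperature is scheduled after D1 to support the SAP's end-of-fever rule, that rule is narrower than the protocol's definition, and the source of the end date is not named.

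The size depends on the rule chosen. With the efficacy item alone and no recalled date, first afebrile days 3 to 5 collapse to D5, and a true one-day difference in medians appears as 0 or about 3 days. If the safety-list answers or a recalled date are used, the distortion is smaller and may vanish for endings up to D5. The simulated percentages rest on assumed distributions and an assumed 100 febrile participants per arm; the enumeration needs only the recording rule. The primary outcome and its sample size are not affected. This is a worthwhile, inexpensive improvement.

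**What to change.** 1. In table 4.3.3, mark the fever item on D3 and D4, as the ordinal scale already is.
2. At each call, record the participant's own axillary temperature that day, or that it was not measured. Once fever has ended, record the date of the last fever day.
3. In SAP 4.2, derive duration from that date and align the end-of-fever rule with the protocol definition, so that it covers subjective fever as well as temperature.
4. For participants already past D4, state in the SAP, before unblinding, whether the fever answers from the safety list are used.

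Cost: two marks in the table and one or two questions on existing calls. The recalled date will carry some error, and participants already past D4 keep coarser data. Items 1 and 4 help only endings up to D5; the date in item 2 is what helps later ones.

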4.3.4 Masking and blinding

Placebo will be administered to half of the research participants. The placebo will consist of a product with the same physical characteristics (taste, smell, texture, appearance) as ivermectin, but without the active ingredient. This placebo will be relabelled so that it looks the same as the investigation drug.

4.3.5 Follow up

To evaluate the evolution of the research participants and determine safety and efficacy according to the primary and secondary outcomes, subjects will be called on days 2, 3, 4, 5, 8, 11, 15 and 21 to fill out a questionnaire. In the event that the research participant requires hospitalization, the research participant will be visited personally to extract the information from the medical record. On the 21st day, the study will finish the evaluation of primary and secondary outcomes. In the case of hospitalized research participants, follow-up will continue until the end of hospitalization to determine their vital status.

4.3.6 Adherence to treatment

The administration of the research product will be done by self-administration in case of outpatient research participants, and in the case of hospitalized participants the administration instructions will be given to the subject and / or the health personnel who attends him/her, complying with the requirements of the institution.

Research participants will be contacted daily by phone call to remind them to take the research product, assess drug adherence, and detect adverse events to the research product.

4.3.7 Measurement of Security Parameters

On the day of the screening visit, all participants will have their liver enzymes measured. The research participant will not be randomized and therefore will not be included in the study if these are elevated > 1.5 times normal values.

In follow-up calls (days 2, 3, 4, 5, 8, 11, 15, and 21), research participants will be asked about symptoms that have historically been reported in subjects receiving ivermectin (uncontrollable shaking of a body part, dizziness, loss of appetite, nausea, vomiting, stomach pain or bloating, diarrhea, constipation, weakness, drowsiness, chest discomfort, swelling (face, arms, hands, feet, ankles, or lower legs), and other symptoms, pain and swelling in joints, painful and swollen glands in the neck, armpit, or groin, fast heartbeat, eye pain, blurred vision, redness or tearing, swelling (face, arms, hands, feet, ankles or calves), pain and swelling in the joints, painful and swollen glands in the neck, armpit or groin, fast heartbeat, pain in the eyes, blurred vision, redness or tearing, swelling of the eyes or eyelids, abnormal

sensation in the eyes, fever, blisters or peeling of skin, rash, hives, and itching) to complete the information requested by the data collection form. The proportion of research participants with adverse events in both arms will be compared.

4.4 Sample size

According to the literature and previous data in this study, 75% of the subjects will have the event of interest (disappearance of symptoms) by day 21. Thus, including 390 subjects, we will identify 290 events of interest. With this sample size we will have a power of 80% and an Alpha of 0.05 to detect a Hazard ratio of 1.4 of ivermectin vs. placebo in time to symptom resolution. Taking into account a 2 % follow-up loss and 76 subjects who will be excluded from the primary analysis¹, we will include a total of 476 subjects in the study.

4.5 Data analysis

An interim analysis will be conducted without breaking the blind when 200 research participants have been randomized. The study will be discontinued if this analysis detects a significant treatment effect on the main objective, if it is detected that a significantly larger group of subjects withdraw from the intervention arm due to adverse events, or if no difference is detected between the two groups. Recruitment will continue while this analysis is performed.

The information will be analyzed with Stata version 14 (SE; Stata corporation, College Station, Texas). For this purpose, subjects will be grouped into 2 groups that comprise

- Group 1:** Subjects who received ivermectin
- Group 2:** Subjects who received placebo.

The baseline characteristics of the subjects will be described by descriptive analysis.

The main analysis will be by intent-to-treat. The time until the disappearance of symptoms will be determined when all research subjects reach day 21. Clinical deterioration or death before the 21st will be right censored- on the 21st. Deaths will be included unless there is strong evidence that the cause of death was not associated with COVID-19. The time until the disappearance of symptoms will be presented in a Kaplan-Meier curve and will be compared with the log-rank test. Hazard Ratios will be calculated with their 95% confidence interval through a Cox proportional-hazards model.

¹ 76 subjects included in the study had errors in the enlistment of the investigation product consecutively for three weeks, and will be excluded from the primary analysis.

Secondary outcomes and adverse events in each of the groups will be expressed by absolute and relative frequencies with their corresponding 95% confidence interval. For the univariate analysis in the quantitative variables, statistical parameters of central tendency and dispersion (means and standard deviations) will be described if the variable has a normal distribution. In case of not having a normal distribution, medians and interquartile ranges will be described. The qualitative variables will be measured and analyzed through proportions with their corresponding 95% confidence interval.

To determine the efficacy of the intervention in secondary outcomes, a bivariate analysis will be performed, evaluating the association of treatment, demographic and clinical variables with the different outcomes.

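### The interim stopping rule has no significance level, futility threshold or adjusted final alpha, so the stated 80% power and 5% alpha cannot both hold if the tests are run at an unadjusted 0.05

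*Supplement*

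**What the plan says.** Protocol 4.5 (Data analysis) sets the timing: "An interim analysis will be conducted without breaking the blind when 200 research participants have been randomized". Three triggers follow. The first is efficacy: "The study will be discontinued if this analysis detects a significant treatment effect on the main objective". The second is significantly more withdrawals for adverse events from the intervention arm. The third reads "or if no difference is detected between the two groups". Recruitment continues while the look is carried out.

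No significance level, boundary, spending function, futility threshold or adjusted final level is given. The final analysis is a log-rank test with a Cox hazard ratio and 95% confidence interval.

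Protocol 4.4 (Sample size), repeated in SAP 2.2, states: "including 390 subjects, we will identify 290 events of interest", and then "With this sample size we will have a power of 80% and an Alpha of 0.05". The latest SAP (20 September 2020) has no interim analysis or stopping rule, and its primary test in 6.1 is unadjusted. An independent data monitoring board is mentioned only in the summary of protocol changes (Amendment 4), in connection with the dispensing error.

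**The concern.** The power and alpha in 4.4 belong to a trial tested once, at about 290 events. The rule in 4.5 adds a second chance to declare efficacy and an undefined way to stop for lack of effect. The first pushes the false-positive rate up; the second pushes power down. How far each moves depends on a threshold that the plan never states, so the choice could be made after the interim data are seen. At stake are a false claim of benefit more often than the declared 5%, or abandonment of a drug that has the planned effect.

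Two further features of the rule are unclear. The look is counted in randomised patients, whereas the information in a log-rank test comes from events, and 76 randomised patients are to be left out of the primary analysis. The look is also to be done with the blind intact, but 4.5 does not say who sees data by arm.

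**Working it through.** **Inputs.** Hazard ratio 1.4, 75% resolved by day 21, 390 analysed, 290 events, 80% power, alpha 0.05, 76 excluded (all Protocol 4.4); 1:1 allocation (4.1.4); look at 200 randomised (4.5). Assumptions: tests are two-sided, and a significant interim result means p<0.05.

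**The plan's own figure.** Power = Φ(ln HR × √d / 2 − 1.96), with ln 1.4 = 0.3365. At d = 290: 0.3365 × 17.03 / 2 = 2.865; 2.865 − 1.96 = 0.905; Φ = 81.7%. The events needed for 80% power are 278 (Schoenfeld) or 283 (Freedman), and 390 × 0.75 = 292.5. The stated figures are therefore reproduced as a single-look design, with no allowance for an interim test.

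**Interim events.** The plan does not give them. If all 200 reach day 21, the expected number is 200 × 0.75 = 150 (information fraction 150/290 = 0.52). If all 76 excluded patients are among the first 200, it is 124 × 0.75 = 93 (0.32).

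**Power at the look alone.**
- d = 150: 0.3365 × 12.25 / 2 − 1.96 = 0.10; Φ = 54%.
- d = 93: 0.3365 × 9.64 / 2 − 1.96 = −0.34; Φ = 37%.

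**Two looks.** Z1 and Z2 are bivariate normal with means ln HR × √d / 2 and correlation √(d1/290). The trial stops for efficacy if |Z1| ≥ 1.96 and for no difference if |Z1| < c; otherwise it is tested at 1.96 with 290 events.
- Type I error = P(|Z1| ≥ 1.96) + P(c ≤ |Z1| < 1.96 and |Z2| ≥ 1.96) at HR 1.
- Power = P(Z1 ≥ 1.96) + P(c ≤ |Z1| < 1.96 and Z2 ≥ 1.96) at HR 1.4.

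By numerical integration:

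| Reading of the no-difference stop | Alpha, 150 events | Power, 150 events | Alpha, 93 events | Power, 93 events |
|---|---|---|---|---|
| Not applied (c = 0) | 8.3% | 83.7% | 8.9% | 83.4% |
| abs. z below 0.67 | 7.8% | 81.3% | 7.8% | 74.5% |
| abs. z below 1.0 | 7.4% | 78.1% | 7.1% | 67.5% |
| abs. z below 1.645 | 5.8% | 64.3% | 5.6% | 47.7% |
| Literal: any non-significant result (c = 1.96) | 5.0% | 54.0% | 5.0% | 36.8% |

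No row has both alpha at or below 5% and power at or above 80%.

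**How often a drug with HR 1.4 is stopped for no difference (150 events).** 8%, 14% and 34% for the three intermediate cut-offs, and 46% on the literal reading (63% with 93 events).

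**With a boundary.** An O'Brien-Fleming type (Lan-DeMets) boundary at 145 of 290 events gives |Z| > 2.96 (p < 0.0031) at the look and p < 0.0490 at the end. Total alpha is 5.0% and power 81.6%, with no binding futility stop. A Pocock boundary at the same point would give power 77.5%.

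**The case against.** The authors plainly did not mean the trial always to end at 200: they plan 476 participants and keep recruiting during the look. The 37–54% power is therefore the extreme of a wide range. With 150 events and a mild futility cut-off such as |z| < 0.67, power stays at 81%. This stands, and the low-power figures should not be read as the expected result.

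A reader might also infer that alpha and power both fail. That is not so in general. On the literal reading alpha stays at 5%; with the no-difference stop unused, power stays above 80%. Both miss their targets only for some intermediate cut-offs.

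A reader might infer that any by-arm comparison contradicts keeping the blind. It does not: a two-sided log-rank test can be run on masked A/B codes, which is enough for the efficacy and no-difference triggers. The trigger on withdrawals from the intervention arm does need arm identity. The phrase may mean only that study staff stay blinded, but 4.5 does not say so.

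Finally, the board might apply a strict interim level, in which case alpha would be close to 5%. Nothing in the documents provides for this. What survives is that the rule as written leaves both error rates undetermined, and that unadjusted 0.05 tests cannot deliver the stated pair.

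**Conclusion.** The point holds and must be fixed, because the rule decides whether the trial continues and whether its primary test is valid. With unadjusted two-sided 0.05 tests, at least one of the two figures in 4.4 fails on every reading computed. The missing efficacy boundary is the sturdier half: unless the no-difference cut-off is severe, alpha is about 7–9%. The power loss ranges from none to severe with the undefined threshold.

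The conclusion rests on three assumptions. Significant means p < 0.05 at the look, since no level is stated. The 150 events are an expected count with all 200 followed to day 21; fewer will be available if some have not reached it. The 93 events are a bounding case that puts all 76 excluded patients in the first 200, which the documents do not establish. They also do not show whether the look has taken place, so nothing here says that a stopping decision was wrongly made.

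**What to change.** State one interim rule, in the same words, in Protocol 4.5 and the SAP:

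- Time the look by primary-outcome events among patients eligible for the primary analysis, for example 145 of 290.
- Give a pre-specified alpha-spending efficacy boundary and the matching final level. The O'Brien-Fleming type above (p < 0.0031, then p < 0.049) is one sound choice; any boundary fixed in advance that holds total alpha at 5% would do.
- Delete the no-difference trigger, or replace it with a numerical, non-binding futility threshold.
- State that the by-arm analysis goes only to the independent data monitoring board, and how arm identity is handled for the withdrawal trigger.
- Restate 4.4 and SAP 2.2 with the power and alpha of the two-look design.
- If the look has already happened, report when, on how many events and by what criterion, and account for the alpha spent.

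The cost is a wording change in two documents and a final level of about 0.049 in place of 0.050. With the example boundary, no extra patients are needed.
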